|  | 
A pharmacogenomics (PGx) substudy will be conducted for exploratory analysis of genetic variations predictive of autoimmune conditions, including thyroid and immune thrombocytopenia (ITP), related to MS disease and/or the effects of alemtuzumab. For research purposes only and on a voluntary basis, a blood sample will be proposed to approximately 300 ongoing patients in the TOPAZ study who have not provided a PGx sample in the previous studies (CAMMS03409, CAMMS223, CAMMS323 and CAMMS324). A blood sample will be collected from consenting patients.
 
Objectives of the substudy are as follows:
 
 
• To develop biomarkers predictive of autoimmune conditions including thyroid disorders and immune thrombocytopenia. This will include collection of samples from patients who have not yet developed any auto immune conditions; these samples would be used as controls.
 
• To explore efficacy and safety markers through data analysis.
 
• To explore genetic variation related to MS disease manifestation through data analysis.
 
 
Sample collection, handling, storage, and analysis will conform to all applicable national guidance and regulations. Details of the PGx sub-study are presented in Appendix C.
 |
| 
STUDY POPULATION
 
Main selection criteria
 
Total expected number of patients
   | 
Inclusion criteria
 
I 01. Patient has completed at least 48 months of the Extension Study CAMMS03409.
 
I 02. Signed written informed consent form (ICF).
 
Exclusion criteria
 
E 01. Patient participating in another investigational interventional study.
 
Approximately (up to) 1248 eligible patients from the Extension Study (CAMMS03409)
 
In approximately (up to) 180 study centers
  |
| 
STUDY TREATMENT(s)
   |  |

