## 4 INTRODUCTION AND RATIONALE

Multiple sclerosis (MS) is a demyelinating disease of the central nervous system (CNS) that affects approximately 2.5 million people worldwide (1). Its clinical course is typically characterized by initial episodes of transient neurological compromise with full recovery, followed by a phase of cumulative deficits that may increase with each new episode. Most relapsing patients eventually develop secondary progression leading to a constellation of chronic sequelae including profound muscle weakness, impaired gait and mobility, bladder and bowel dysfunction, and cognitive and visual impairments.

MS is believed to arise from the interplay of polygenic inherited susceptibility and as yet unidentified environmental agents. Age of onset typically ranges from 10 to 59 years, with most cases occurring between 20 and 40 years of age. As with most other autoimmune disorders, MS is more than twice as common among women. Pathologically, MS is characterized by focal and non-focal tissue injury of the brain and spinal cord due to the complex interplay of inflammation, demyelination, axonal injury, astrogliosis, and tissue atrophy. Lymphocytes are believed to play a central role in MS pathogenesis.

Alemtuzumab (Lemtrada®) is a humanized monoclonal antibody that binds to CD52, a cell surface antigen present at high levels on T and B lymphocytes, and at lower levels on natural killer cells, monocytes, and macrophages (2).

There is little or no CD52 detected on neutrophils, plasma cells, or bone marrow stem cells. Alemtuzumab acts through antibody-dependent cellular cytotoxicity and complement mediated lysis following cell surface binding to T and B lymphocytes.

The mechanism by which alemtuzumab exerts its therapeutic effects in MS is unknown, but may involve immunomodulation through the depletion and repopulation of lymphocytes.

Research suggests that potential immunomodulatory effects in MS may include alterations in the number, proportions, and properties of some lymphocyte subsets post-treatment (3).

Pilot studies in MS patients were conducted at Addenbrooke's Hospital in the United Kingdom (UK). Genzyme Corporation (Genzyme, a Sanofi company) has sponsored Phase 2 and Phase 3 randomized, comparator-controlled studies in patients with relapsing remitting MS that have established superior efficacy for alemtuzumab compared with subcutaneous interferon beta-1a (SC IFNB-1a, Rebif®) on clinical and imaging endpoints (4, 5, 6, 7, 8).

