## INCREASE IN ALT

### ACUTE RENAL FAILURE

### SUSPICION OF RHABDOMYOLYSIS

## **Appendix C Exploratory pharmacogenomics assessment substudy**

### **Background information**

The autoimmunity adverse events associated with LEMTRADA are identified potential risks and pose a potential barrier to a greater use of the product, including autoimmune thyroid disorders (36%), immune thrombocytopenia (ITP; 2%), and nephropathies (0.3%). If biomarkers for autoimmunity were known, more patients could potentially benefit from LEMTRADA treatment.

A team effort has been under way to discover a panel of biomarkers that could predict which patients are at risk of developing autoimmunity events. Blood samples collected from LEMTRADA-treated MS patients within clinical studies were preserved for biomarker discovery. Genomics and proteomics profiling were conducted on a cohort of LEMTRADA-treated MS patients, including patients who developed treatment-emergent autoimmune disorders and patients who, to date, have not developed such disorders. The search for the associated markers was focused on single nucleotide polymorphism (SNP), human leukocyte antigen (HLA)-allele, HLA-amino acid polymorphism, serum cell-free microRNA, serum protein, and serum autoantibody.

Correlative analysis of this biomarker data with the development of autoimmune conditions indicated no robust signals for protein biomarkers. Interestingly, we identified candidate SNPs that are potentially associated with the development of ITP with this preliminary discovery data set. Although potential predictors have been identified, more samples are needed to validate this data. Samples from the TOPAZ study together with samples from patients from previous clinical trials (CAMMS03409, CAMMS223, CAMMS323 and CAMMS324) and from post-marketing patients will provide a large enough cohort to validate the to validate the preliminary findings (and potentially efficacy/non-responders). Samples from patients who have not yet developed any autoimmune conditions would be used as controls.

The goal of this exploratory substudy is to obtain additional data to identify a biomarker for autoimmune events so that LEMTRADA can be safely administered to patients who need the treatment.

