  - Temporally associated\* cervicocephalic arterial dissection  
(\* Temporally associated: 1 to 3 days after the last infusion)
  - Serious infections including serious opportunistic infections (eg, Listeria infections, CMV, EBV), HPV associated with cervical dysplasia
  - Malignancy.
  - Pneumonitis

The standardized MedDRA queries (SMQ) or Custom MedDRA queries (CMQ) will be applied as appropriate to select AESIs.

**Infusion-associated reactions (IAR)** is defined as any adverse event occurring during and within 24 hours of alemtuzumab infusion. It will be analyzed separately for retreated patients.

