## **2.3 ANALYSIS POPULATIONS**

### **2.3.1 Safety populations**

All patients who have signed the ICF will be included in the safety population.

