#### **2.4.5 Analyses of safety data**

The summary of safety results will be presented in overall group and by subgroups (IAT vs DAT).

Only data collected in TOPAZ study will be used for analysis in addition of baseline information from previous studies.

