#### **2.4.5.1 Analyses of adverse events**

##### ***Generalities***

All the reported AE will be considered as treatment emergent adverse event (TEAE).

Adverse event incidence tables will present by SOC, HLGT, HLT, and PT, sorted in alphabetical order in overall group and by subgroups (IAT vs DAT), the number (n) and percentage (%) of patients experiencing an adverse event. Multiple occurrences of the same event in the same patient will be counted only once in the tables. The denominator for computation of percentages is the safety population in overall group and by subgroups (IAT vs DAT).

Sorting within tables ensures the same presentation for the set of all adverse events within the observation period. For that purpose, the table of all treatment-emergent adverse events presented by SOC and PT sorted by the internationally agreed SOC order and decreasing frequency of PTs in overall group within SOCs will define the presentation order for all other tables unless otherwise specified.

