### ***Analysis of adverse events of special interest (AESI)***

- All treatment-emergent adverse events of special interest by primary SOC, HLG, HLT, and PT, showing the number (%) of patients sorted by the internationally agreed SOC order. The other levels (HLG, HLT, PT) will be presented in alphabetical order
- All treatment-emergent adverse events of special interest by primary SOC and PT, showing the number (%) of patients with at least 1 treatment-emergent adverse event, sorted by the internationally agreed SOC order and by decreasing incidence of PTs within each SOC. This sorting order will be applied to all other tables, unless otherwise specified
- All treatment emergent adverse events of special interest by PT, showing the number (%) of patients, sorted by decreasing incidence of PT
- The event rate per patient-year (the number of events in question divided by total treatment exposure in patient years) for non-temporary AESI(s) will be provided by SOC and PT
- The frequency of treatment-emergent adverse events over time will be provided for the non-temporary treatment-emergent AESIs, where the time intervals will be defined as: <2 courses, 2 – 4 courses, 4 – 6 courses, 6 – 8 courses, etc. In each time interval, the denominator for calculation of percentage will be the number of patients who entered the time interval and the numerator will be the number of patients with at least 1 treatment emergent AESI occurring in this time interval. Note that only the first event will be counted and all recurrent events will not be included
- For retreated population, the frequency of treatment-emergent temporary adverse events over time will be provided for the temporally associated AESIs (pulmonary alveolar hemorrhage, myocardial ischemia, myocardial infarction, stroke, cervicocephalic arterial dissection), where the time intervals will be defined as: during alemtuzumab infusion day 1, during alemtuzumab infusion day 2, during alemtuzumab infusion day 3, 1 day after alemtuzumab infusion, 2 days after alemtuzumab infusion and 3 days after alemtuzumab infusion. In each time interval, the denominator for calculation of percentage will be the number of patients who entered the time interval and the numerator will be the number of patients with at least 1 treatment emergent AESI occurring in this time interval. Note that only the first event will be counted and all recurrent events will not be included

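### AESI percentages use the whole safety population as denominator, so the SAP gives no new-onset incidence among patients at risk and dilutes the women-only events

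*SAP*

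**What the plan says.** The denominator rule is in SAP 2.4.5.1, Generalities: "The denominator for computation of percentages is the safety population in overall group and by subgroups (IAT vs DAT". SAP 2.3.1 defines that population: "All patients who have signed the ICF will be included in the safety population". It carries no restriction by sex or by earlier event. (The general rules in SAP 2.4.5 cite section 2.3.1.1, which is headed as the retreated population. I read this as a slip for 2.3.1, because the text names the safety population.)

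The data source is limited in SAP 2.4.5: "Only data collected in TOPAZ study will be used for analysis in addition of baseline information from previous studies".

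The AESI part of 2.4.5.1 contains three kinds of summary:
- Incidence tables count patients with at least one event reported in TOPAZ, over the safety population.
- Rates per patient-year divide events by total treatment exposure.
- Two over-time tables divide by the patients entering each interval. Only here does the SAP add: "Note that only the first event will be counted and all recurrent events will not be included".

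None of the three excludes patients who had the condition before TOPAZ, and none is limited to women. Yet the AESI list in SAP 2.1.4.1 includes pregnancy in a female participant and "HPV associated with cervical dysplasia".

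The handling of carried-over events is not consistent. Protocol 10.1.1 and 10.4.2 have events still ongoing from CAMMS03409 recorded at Visit 1, and SAP 2.4.5.1 treats every reported event as treatment-emergent. Protocol 10.4.1.4 says that conditions present at Visit 1 which do not worsen are not adverse events.

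**The concern.** Long-term safety is the primary objective, and AESI incidence is a primary endpoint (protocol 9.1). Protocol 11.4.2 promises particular attention to the development of autoimmune disorders, and names ITP, thyroid disorders and anti-GBM disease. Development means new onset in people who do not yet have the condition.

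By SAP 1.4, patients reach TOPAZ after 2 years in the original studies and at least 4 years in the extension. A fair number may already have an autoimmune thyroid disorder. They remain in the denominator, and whether they also appear in the numerator depends on which recording rule a site follows. The resulting percentage does not tell a patient who has so far escaped the condition what the later risk is.

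The planned display by IAT and DAT is also exposed. IAT patients began alemtuzumab in the original studies and DAT patients in the extension (SAP 2.3.3), so their shares of prior cases may differ. The documents do not allow that difference to be sized.

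The SAP applies at-risk reasoning elsewhere. Denominators for potentially clinically significant abnormalities (PCSAs) are the patients assessed for the parameter (SAP 2.4.5), laboratory PCSAs are split by baseline status (SAP 2.4.5.3), and HPV testing is marked as for women only (SAP Table 2). The AESI tables get none of this.

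**Working it through.** The plan states no AESI incidence or sample size calculation, so there is no sponsor figure to reproduce.

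**Inputs**
- Planned size, protocol summary: "Approximately (up to) 1248 eligible patients from the Extension Study (CAMMS03409", so N is at most 1248.
- Background shares, protocol Appendix C: "including autoimmune thyroid disorders (36%), immune thrombocytopenia (ITP; 2%), and nephropathies (0.3" per cent. These describe the alemtuzumab programme, not patients at TOPAZ entry. The thyroid share is therefore varied from 20% to 40%.
- Sex, protocol section 4: "MS is more than twice as common among women". This is general background and puts men below one third. The TOPAZ split is not given, so 25% to one third is assumed.

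**Women-only events.** Let m be the share of men. No man can be in the numerator, so table % = (1 − m) × women-only %, and women-only % / table % = 1/(1 − m).
- m = 25%: 312 men, 936 women; 1/0.75 = 1.33.
- m = one third: 416 men, 832 women; 1/0.667 = 1.50.

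The direction is certain. Only the size depends on m, and 1.50 is a ceiling if the background ratio holds in TOPAZ.

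**Prior cases, none in the numerator.** Let p be the share with the condition before TOPAZ. At-risk % / table % = 1/(1 − p).
- Thyroid, p = 20%: 1/0.80 = 1.25. p = 36%: 1/0.64 = 1.56 (449 prior cases, 799 at risk). p = 40%: 1/0.60 = 1.67.
- ITP, p = 2%: 1/0.98 = 1.02 (25 prior cases).
- Nephropathies, p = 0.3%: 1/0.997 = 1.003 (4 prior cases).

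**Prior cases partly in the numerator.** Let f be the fraction of prior cases also counted in TOPAZ, through an ongoing or repeat event, and q the incidence among those at risk. Then table % = p × f + (1 − p) × q. This understates q only when f < q. With p = 36% and illustrative values of q:

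| q | f = 0 | f = 5% | f = 10% | f = 50% |
|---|---|---|---|---|
| 5% | 3.2% | 5.0% | 6.8% | 21.2% |
| 10% | 6.4% | 8.2% | 10.0% | 24.4% |

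For q = 5% and f = 10%: 0.36 × 0.10 + 0.64 × 0.05 = 0.068. The same percentage can fall below or far above the at-risk incidence, depending on a counting rule that the documents leave open.

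**Does the patient-year rate help?** No. It keeps prior cases in the exposure and does not stop the clock at the first event. SAP 2.4.3.1 measures person-years from first treatment in the prior studies, not from TOPAZ entry.

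**The case against.** The strongest reply is that a percentage of the whole cohort is a valid description. The endpoint is AESI incidence, not first-ever incidence, and the safety analysis is meant to be descriptive. Sex is tabulated overall and by subgroup, so a reader can rescale the women-only rows by hand. This stands in part: the crude tables are not an error and should stay. But no planned table gives the number with a prior autoimmune event, so a reader cannot rescale the thyroid rows at all.

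A reader might infer from the 36% figure that AESI percentages in general are understated by about a third. The documents do not support that, for four reasons:
- The 36% is a programme figure from the pharmacogenomics appendix, given without population or follow-up time.
- For ITP and nephropathies the corresponding dilution is about 2% and 0.3%. For women-only events a third is an upper limit.
- First-event-only counting applies to the over-time tables alone. Elsewhere a patient with an earlier thyroid disorder can still be counted, for example after worsening or under a different preferred term. A category-level share also does not carry over to each preferred-term row.
- If carried-over cases are counted, the thyroid figure may be too high rather than too low.

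It is also fair that a merge with earlier data departs from the TOPAZ-only rule. Protocol 10.1.1 confirms a common patient number only with CAMMS03409. However, SAP 2.4.4 already plans to obtain relapse data from CAMMS323, CAMMS324 and CAMMS03409, so linkage to those studies is foreseen. Linkage to CAMMS223 would need confirming.

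**Conclusion.** The concern holds in limited form. The SAP does not provide new-onset incidence among patients still at risk, which is what protocol 11.4.2 leads the reader to expect.

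- **Pregnancy and HPV-associated cervical dysplasia:** understatement is certain. The factor of 1.33 to 1.5 rests on the assumed 25% to 33% men.
- **Thyroid disorders:** the percentage is not a new-onset incidence under either reading of the recording rules. The factor of 1.25 to 1.67 rests on an assumed 20% to 40% prior cases with none counted. If carried-over cases are counted, the sign can reverse. The direction stays unknown until the rules are reconciled.
- **ITP and nephropathies:** the denominator effect can be ignored.

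The change is worth making before database lock. It bears on the primary objective and replaces a stated rule with a more informative one at modest cost.

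**What to change.** In SAP 2.4.5.1:
1. Reconcile protocol 10.4.1.4 with protocol 10.4.2 and the SAP's treatment-emergent rule. State whether an event carried over from CAMMS03409 enters the AESI numerators, and show such events separately from new onsets.
2. Use the number of women in the safety population, overall and in IAT and DAT, as denominator for pregnancy and HPV-associated cervical dysplasia.
3. For each chronic autoimmune AESI category, thyroid disorders above all, add first-ever incidence and a rate per patient-year. Include only patients with no event in that category in CAMMS223, CAMMS323, CAMMS324 or CAMMS03409. Start person-time at TOPAZ entry and end it at the first event, or at the end of TOPAZ follow-up if there is none. Report the number of prior cases excluded, by IAT and DAT.
4. State item 3 as an exception to the TOPAZ-only rule in SAP 2.4.5.
5. Keep the planned crude tables.

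The cost is SAP wording, a merge with the adverse event history of the earlier studies, and a few extra tables. Item 2 needs no new data. The women-only percentages will rise; the thyroid figures may move either way.

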### **6.2.2 Determination of end of clinical trial (all patients)**

The end of the clinical trial occurs 5 years (plus a window of 6 months) after the inclusion of the first patient.

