#### 10.1.4 End of study (EOS) visit

This visit will be performed in one of the following situations:

- At the end of the study. This visit corresponds to the Visit M60 $\pm$ 14D.
- At the end of the study period of 5 years, for all the ongoing patients, the next scheduled site visit will be changed into an EOS visit.
- If the patient is prematurely withdrawn from the study.

The following items will be checked/performed and recorded:

- Safety assessments ([Section 9.5](#)).
  - AE collection.
  - Vital signs and physical examination.
- Efficacy assessments ([Section 9.6](#)).
  - MS relapse verification.
  - EDSS.
  - Brain imaging to include: G-MRI, MRI-T1 and MRI-T2 T1 pre- and post-Gadolinium (Gd), T2/PD, FLAIR and T1 sagittal sequences (only if not performed in the previous 6 months).
  - Health questionnaires: SF-36, FAMS and EQ-5D.
- Pharmaco-economic assessment: modified HRUQ/HRPQ ([Section 9.7](#)).
- Concomitant medication.
- Blood sample collection for pharmacogenomic analysis (for consenting patients only).  
Omit if already collected during a prior study visit.

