### 1.4 STUDY PLAN

The whole clinical trial of alemtuzumab consists of three study periods:

CAMMS223/323/324 prior studies (2 years): to compare the efficacy and safety of alemtuzumab to subcutaneous (SC) interferon beta-1a (IFNB-1a, Rebif) in treatment-naïve patients with relapsing-remitting multiple sclerosis (RRMS) who had recent MS disease activity as demonstrated by clinical relapses.

CAMMS03409 extension study (at least 4 years): to examine the long-term efficacy and safety of alemtuzumab in MS patients who received alemtuzumab during prior studies CAMMS223/323/324 and the efficacy and safety of 2 fixed annual alemtuzumab courses in patients who previously received SC IFNB-1a during prior studies.

LPS13649 (TOPAZ) extension study (5 years): to evaluate the long-term safety, efficacy and Quality of life (QoL) of alemtuzumab in patients who have completed at least 48 months of the extension study CAMMS03409.

- ★ Only for patients treated with alemtuzumab: monthly laboratory safety variables collection for 48 months after last infusion
  - For patients who received alemtuzumab in CAMMS03409 study less than 48 months before entering in LPS13649 study, and
  - For patients receiving retreatment with alemtuzumab during the LPS13649 study
- \* After completion of 5 years of the first patient inclusion, the next scheduled visit for any patient will be performed as EOS visit.

Scheduled visits for safety and efficacy assessments will be performed every six months. AEs and concomitant medications will be monitored continuously. Quality of life, pharmaco-economic data and brain imaging will be collected every twelve months (Table 1).

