#### ***Analysis of all treatment emergent serious adverse event(s)***

- All treatment-emergent serious adverse events by primary SOC, HLGT, HLT, and PT, showing the number (%) of patients with at least 1 serious treatment-emergent adverse event, sorted by the internationally agreed SOC order. The other levels (HLGT, HLT, PT) will be presented in alphabetical order
- All treatment-emergent serious adverse events by primary SOC and PT, showing the number (%) of patients with at least 1 treatment-emergent adverse event, sorted by the internationally agreed SOC order and by decreasing incidence of PTs within each SOC. This sorting order will be applied to all other tables, unless otherwise specified
- All treatment-emergent serious adverse events regardless of relationship and related to IMP, by primary SOC, HLGT, HLT, and PT, showing the number (%) of patients with at least 1 treatment-emergent serious adverse event, sorted by the internationally agreed SOC order. The other levels (HLGT, HLT, PT) will be presented in alphabetical order
- The event rate per patient-year (the number of events in question divided by total treatment exposure in patient years) will be provided for SAEs by SOC and PT
- By-patient listing of treatment-emergent SAEs showing analysis group (IAT vs DAT), patient ID, time since first dose of Alemtuzumab infusion in years, age, gender, race, primary SOC decode, PT decode, verbatim (diagnosis), onset date and study day, date of death (if relevant), recovery date/time, event duration, outcome, intensity/grade, relationship to study treatment, action taken with study treatment AE serious criteria.

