#### **2.4.5.2 Deaths**

The following summaries of deaths will be generated for the safety population.

- Number (%) of patients who died by study period (on-study, poststudy)
- Deaths in nonrandomized patients or randomized but not treated patients
- Treatment-emergent adverse events leading to death (death as an outcome on the adverse event case report form page as reported by the Investigator) by primary SOC , HLGT, HLT, and PT showing number (%) of patients sorted by internationally agreed SOC order, with HLGT, HLT, and PT presented in alphabetical order within each SOC .

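### TEAEs and deaths are reported only as crude percentages of all consented patients although the calendar end gives unequal follow-up, so these figures have no defined time horizon

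*SAP*

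**What the plan says.** **End of follow-up.** Protocol 6.2.2: "The end of the clinical trial occurs 5 years (plus a window of 6 months) after the inclusion of the first patient". SAP 1.4: "After completion of 5 years of the first patient inclusion, the next scheduled visit for any patient will be performed as EOS visit". Protocol 10.1.4 agrees: "for all the ongoing patients, the next scheduled site visit will be changed into an EOS visit". Scheduled visits are 6-monthly. SAP 1.4 nevertheless introduces the study as "LPS13649 (TOPAZ) extension study (5 years): to evaluate the long-term safety, efficacy and Quality of life (QoL) of alemtuzumab", and SAP 2.5.3 windows its visits up to TOPAZ Month 60.

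**Denominator.** SAP 2.3.1: "All patients who have signed the ICF will be included in the safety population". SAP 2.4.5.1, Generalities: "The denominator for computation of percentages is the safety population in overall group and by subgroups (IAT vs DAT". The tables of all TEAEs, of related TEAEs and of TEAEs by maximal severity are numbers and percentages of patients. For deaths, SAP 2.4.5.2 plans: "Number (%) of patients who died by study period (on-study, poststudy".

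**Where person-time is used.** For SAEs, SAP 2.4.5.1 adds: "The event rate per patient-year (the number of events in question divided by total treatment exposure in patient years) will be provided for SAEs". It plans the same rate for non-temporary AESIs. Person-years in SAP 2.4.3.1 run between first study treatment in the prior studies and the end of TOPAZ, with the subtraction written in reverse. SAP 2.4.5 restricts safety data to those collected in TOPAZ, apart from baseline information.

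**Withdrawals.** Protocol 10.3.4 leaves the treatment of patients lost to follow-up to the SAP. SAP 2.5.2 (missing data) contains no rule for them.

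**The concern.** Long-term safety is the primary objective, and incidence heads the list of primary endpoints. A percentage means something definite only when the period it covers is known. Here that period varies by patient, with entry date and with withdrawal, and the part of it that nobody observed enters the percentage as event-free.

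Mortality is the clearest case. It is a headline long-term safety figure, and no rate or survival estimate is planned for it. The IAT and DAT percentages are also hard to compare if the two groups differ in follow-up, and the SAP plans no summary of follow-up that would show this. It uses time-based methods elsewhere: Kaplan-Meier for relapse and for time to liver-test elevation, and at-risk denominators for AESI intervals.

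**Working it through.** The documents state no expected incidence, accrual period or withdrawal rate, so there is no plan figure to reproduce. The check is how far a crude percentage falls below the 5-year risk over a range of assumptions.

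**Inputs from the documents:** calendar close at 60 months from first entry; the next 6-monthly visit becomes EOS; Month 60 is the last planned visit.

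**Assumptions:** uniform accrual over A months, constant event hazard, withdrawal independent of events, visits on their target dates.

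**Step 1. Last visit.** For entry *a* months after the first patient, last visit = min(60, next 6-monthly visit after 60 − *a*).

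- *a* under 6: M60
- 6 to under 12: M54
- 12 to under 18: M48
- 18 to under 24: M42

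The share that cannot reach M60 is (A − 6)/A for A of at least 6: 0, 14%, 50%, 67% and 75% for A = 6, 7, 12, 18 and 24.

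**Step 2. Calendar rule alone, true 5-year risk 20%.** Risk by month *m* = 1 − 0.8^(*m*/60): 20.00% at M60, 18.20% at M54, 16.35% at M48, 14.46% at M42. The expected crude percentage is the average over entry bands. For A = 12 it is (20.00 + 18.20)/2 = 19.1%. For A = 24 it is (20.00 + 18.20 + 16.35 + 14.46)/4 = 17.25%.

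**Step 3. Add 5% annual withdrawal (assumed).** With yearly hazards h = −ln(0.8)/5 = 0.0446 and k = −ln(0.95) = 0.0513, the observed risk over *f* years is h/(h+k) × [1 − exp(−(h+k)*f*)]. At 5 years this is 0.465 × 0.381 = 17.7%.

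| Accrual (months) | Crude %, no withdrawal | Relative shortfall | Crude %, 5%/year withdrawal | Relative shortfall |
|---|---|---|---|---|
| 6 | 20.0 | 0 | 17.7 | 11% |
| 7 | 19.7 | 1% | 17.5 | 12% |
| 12 | 19.1 | 5% | 17.0 | 15% |
| 18 | 18.2 | 9% | 16.3 | 19% |
| 24 | 17.25 | 14% | 15.5 | 22% |

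For a true 2% risk, the calendar rule alone gives 1.90% at 12 months' accrual and 1.70% at 24 months' (5% and 15% low). For very common events the effect is small: at a true 90% with 12-month accrual and no withdrawal, the shortfall is 1.4%.

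**Step 4. The existing patient-year rates.** If the total treatment exposure in the rate means the person-years of SAP 2.4.3.1, TOPAZ events are divided by time that includes at least 2 + 4 = 6 years before TOPAZ (durations from SAP 1.4). The ratio to the TOPAZ rate is t/(6 + t): 5/11 = 0.45 at t = 5 years and 4/10 = 0.40 at t = 4 years. The rate would be about 55% to 60% too low.

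**The case against.** **No table claims to be a 5-year risk.** The analysis is descriptive, and n (%) over the observation period is a legitimate summary of what was reported. This stands. A reader might infer that the primary incidence is simply understated. The documents do not support that: the shortfall exists only against a 5-year risk that the SAP does not say it estimates. The description of TOPAZ as a 5-year study does, however, invite that reading.

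**SAEs and AESIs are partly covered.** This also stands. It would be wrong to list SAEs as having a crude percentage only. The limits are that the rate counts events rather than patients, and that its person-time may not match its events.

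**The direction for TEAEs is unclear.** Every reported AE counts as a TEAE (SAP 2.4.5.1). AEs ongoing from CAMMS03409, or arising before Visit 1, are recorded in TOPAZ (Protocol 10.1.1 and 10.4.2). That pushes the TEAE percentage up, against the loss from short follow-up, so the net sign is unknown. Deaths are not affected.

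**The calendar effect may be small.** It is zero if everyone entered within 6 months. It would be a mistake to attribute the 12% to 22% shortfalls in the table to the calendar rule, because the assumed withdrawal alone accounts for 11%. The March 2016 US amendment, which widened the entry window, suggests that enrolment was then open there. The first patient's date is not given, so no accrual length follows.

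**Vital status may be known after withdrawal.** Protocol 10.3.4 asks sites to seek it for patients who do not return, and SAP 2.4.5.2 tabulates poststudy deaths. The withdrawal figures may therefore overstate the loss for mortality.

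**Conclusion.** The point holds in a limited form. Follow-up is unequal by design, and the TEAE tables (overall, related, by severity) and the death table carry no time dimension. Their percentages have no defined horizon. For deaths and new-onset events they fall below the 5-year incidence whenever some patients are observed for less than 5 years. For TEAEs as the SAP defines them, the net direction cannot be stated.

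For a true 20% risk, the calendar rule costs between 0 and about 14% in relative terms over accrual periods of 6 to 24 months, and 5% annual withdrawal alone about 11%. These figures rest on uniform accrual, constant hazard and non-informative withdrawal, none of which the documents state. The person-year mismatch in the existing SAE and AESI rates could be larger, at about 55% to 60%, but only if SAP 2.4.3.1 supplies their denominator. The change is worth making because it is cheap and gives the primary safety and mortality figures a stated period.

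**What to change.** In SAP 2.4.5.1 and 2.4.5.2, keep the n (%) tables and add:

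1. **Deaths:** Kaplan-Meier cumulative mortality from D1, for example at 12, 24, 36, 48 and 60 months, with 95% CI and numbers at risk. Censor at EOS or withdrawal, or at last known vital status if that is used for all patients, alive or dead.
2. **TEAEs with onset on or after D1 (any, related, severe):** cumulative incidence with death as a competing event, censored at EOS or withdrawal, plus patients with a first event per 100 patient-years of TOPAZ follow-up. The onset restriction is needed because carried-over events have no valid time from D1.
3. **Follow-up:** its distribution overall and for IAT and DAT.
4. **Person-years:** TOPAZ-only time for every rate, including the planned SAE and AESI rates. Correct the reversed subtraction in SAP 2.4.3.1.

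Also state how patients lost to follow-up are handled, as Protocol 10.3.4 requires. Correct the reference in SAP 2.4.5 that defines the safety population by Section 2.3.1.1, which is the retreated population; 2.3.1 is meant.

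Cost: SAP wording and a few extra tables from dates already collected, with no change to conduct. Intervals will be wider at late time points, where fewer patients remain at risk.
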